## 10.9.1 MONITORING REPORTS

After each monitoring visit, the Monitor will send to the Investigator an e-mail or letter summarizing the monitoring visit. A monitoring report will be sent to the Sponsor. The report will include:

- Date of the monitoring visit
- Monitor name
- Site name
- Investigator name
- Individual names present for visit
- Items reviewed during the visit, findings, and any required follow-up

The Investigator will be responsible for ensuring that follow-up action items requiring resolution at the site are completed in an accurate and timely manner.

## 10.10 DIRECT ACCESS TO SOURCE DOCUMENTS

By participating in this research study, the Investigator agrees to permit monitoring and auditing by the Sponsor and/or its designee(s) and inspection by applicable regulatory authorities. The Investigator also agrees to allow the Sponsor's Monitors/Auditors/FDA Investigators to have direct access to (and copying of, if appropriate) his/her research-related study records (e.g., medical records, source documentation, and billing information) for review to ensure study integrity and data validation.

If an Investigator is notified of a pending investigation by a regulatory agency, standards organization, or other similar organization, he/she will inform the Sponsor promptly.

#### 10.11 ON-SITE AUDITS

Representatives of the Sponsor may visit the study site(s) to conduct an audit of the Study in compliance with regulatory guidelines and company policy. These audits will require access to all study records, including source documents, for inspection and comparison with the CRFs. Subject privacy will be respected.

Similar auditing procedures may also be conducted by agents of any regulatory body reviewing the results of the Study in support of a regulatory submission. The Investigator agrees to immediately notify the Sponsor if he/she has been contacted by a regulatory agency concerning an upcoming inspection.

### 10.12 RECORD STORAGE AND RETENTION

#### 10.12.1 INVESTIGATOR RECORD RETENTION

The Investigator shall maintain all study documentation in his/her possession and/or control and institute measures to prevent accidental or premature destruction any data and/or documents related to the Study.

After discontinuation of the Study, the Investigator shall retain study documentation for a minimum of three (3) years or in accordance with the GCP.

No study document will be destroyed without prior written agreement between the Sponsor and the Investigator. Should the Investigator wish to assign the study records to another party or move them to another location, advance written notice must be given to the Sponsor.

#### 10.12.2 SPONSOR RECORD RETENTION

The Sponsor will maintain all study documentation in its possession and/or contact and institute measures to prevent accidental or premature destruction of any data and/or documents related to the research Study.

The Sponsor shall retain the study documentation for at least ten (10) years after formal discontinuation of Study or 10 years after the last FlowTriever2 Catheter has been placed on the market (whichever is longer).

## 11 ETHICS AND CONFIDENTIALITY

#### 11.1 ETHICAL CONDUCT OF THE STUDY

This Study is to be conducted in accordance with U.S. and international standards for GCP, as described in the following documents:

- ICH Harmonized Tripartite Guidelines for Good Clinical Practice
- U.S. Code of Federal Regulations (CFR) regarding clinical studies (21 CFR including parts 812, 50, 54, and 56)
- The Declaration of Helsinki concerning medical research in humans (64th WMA General Assembly, Fortaleza, October 2013)
- ISO 14155

The Investigator agrees by participating in the conduct of this protocol to adhere to the instructions and procedures described and to adhere to the principals of GCP.

#### 11.2 INSTITUTIONAL REVIEW BOARDS (IRB)

The Sponsor and/or Investigator must submit this protocol to the appropriate IRB. The informed consent form (ICF) used by the Investigator must be reviewed and approved by the Sponsor prior to submission to the appropriate IRB for approval. The Sponsor must also approve all IRB requested changes to the ICF prior to finalization.

This study must be approved by an appropriate IRB/EC at each registry site. Securing the approval is the responsibility of the Investigator, as defined by ICH E6, ISO 14155 and FDA regulations (21 CFR Part 56), prior to starting the study.

The IRB and/or Investigator is required to forward to the Sponsor a copy of the IRB approval to begin the Study. The Study (study number, protocol title, and version) documents reviewed (e.g., protocol, ICF, etc.) and the date of the review should be clearly stated on the written IRB approval. The Study will not start and subjects will not be enrolled until a copy of written and dated approval has been received by the Sponsor.

Any amendment or modification to the protocol should be sent to the IRB. The IRB should also be informed of any event likely to affect the safety of subjects or the conduct of the Study.

#### 11.3 STUDY PATIENT CONFIDENTIALITY

The Investigator must ensure that the privacy of all patients, including their personal identity and all personal health information. In CRFs and other documents, patients will not be identified by their names, but by an individual identification code (i.e., patient identification number).

Personal medical information may be reviewed for the purpose of verifying data recorded in the CRFs. A monitor or Sponsor designee may conduct source-document verification on behalf of the Sponsor, the quality assurance unit, or regulatory authorities. Personal medical information will always be treated as confidential and handled in compliance with the Health Insurance Portability and Accountability Act (HIPAA).

FLARE-FT2 Study CONFIDENTIAL Page 51 of 60

## 11.4 INVESTIGATOR RESPONSIBILITIES

Investigator responsibilities include, but are not limited to, the following:

- Conducting the study in accordance with this investigational plan, signed agreement, and applicable regulations protecting the rights and safety of study patients
- Ensuring that informed consent is obtained for each study patient in accordance with applicable regulations (e.g., ICH E6, ISO 14155, 21 CFR Part 50)
- Ensuring that IRB/EC approval is secured prior to starting the study and ensuring continuing review and approval as required throughout the investigation
- Ensuring all associates, colleagues, and employees assisting in the conduct of the study are informed about their obligations, are adequately qualified and trained, and meet their commitments
- Maintaining adequate and accurate records and ensuring those records are available for inspection at any time
- Ensuring that conducting the study does not give rise to a conflict of interest (financial disclosure is required)

#### 11.5 PUBLICATION POLICY

Publications from the FT2 Study will be handled according to Standard Operating Procedures and as indicated in the CTA.

Clinical study results will be maintained by the following means:

- A final report, describing the results of all objectives and analysis, will be distributed to all Investigators, IRBs and the FDA
- Registering and posting the study results on ClinicalTrials.gov based on the posting rules stipulated
- Submitting for publication the primary study results after the study ends
- Disclosing conflicts of interest (e.g., financial) of the co-authors of publications according to the policies set forth by the corresponding journals and conferences
- Making an individual study sites study data accessible to the corresponding Investigator after the completion of the study, if requested

# 12 TERMS AND DEFINITIONS

Term	Definition	
	Primary Safety Definitions	
Clinical Deterioration	Clinical deterioration will include treatment-related events, such as unplanned endotracheal intubation, unexpected requirement for mechanical ventilation, arterial hypotension (>1 hour or requiring vasopressors) or shock, cardiopulmonary resuscitation, persistent worsening in oxygenation, and emergency surgical embolectomy.	
Device Related Death	Device-related death is defined as any death directly related to thedevice not performing as expected. Device-related death would include death from:  Vascular or cardiovascular injury  Device malfunction  Device-induced cardiac arrhythmia	
Life Threatening or Disabling Bleeding (VARC-2)	
 
Fatal bleeding, OR
 
Bleeding in a critical organ, such as intracranial, intraspinal, intraocular, or pericardial necessitating pericardiocentesis, or intramuscular with compartment syndrome, OR
 
Bleeding causing hypovolemic shock or severe hypotension requiring vasopressors or surgery, OR
 
Overt source of bleeding with drop in hemoglobin ≥5 g/dL or whole blood or packed red blood cells (RBCs) transfusion ≥ 4 units*
 
	
Major Bleeding (VARC- 2)	Overt bleeding that is:  Associated with a drop in the hemoglobin level of at least 3 g/dL, OR  Requires transfusion of 3 units of whole blood/RBC, OR  Causes hospitalization, permanent injury, or requiring surgery, AND  Does not meet criteria of life-threatening or disabling	
Minor Bleeding (VARC- 2)	Any bleeding worthy of clinical mention (e.g., access site hematoma) that does not qualify as life-threatening or disabling bleeding or major bleeding.	
Pulmonary Vascular Injury	Pulmonary vascular injury is defined as perforation or injury of a major pulmonary arterial branch during the index procedure requiring intervention, including but not limited to blood transfusion, open or endovascular intervention, to avoid permanent injury.	
Cardiac Injury	Cardiac injury is defined as any damage to the heart during the index procedure requiring intervention, including but not limited to blood transfusion, open or endovascular intervention, to avoid permanent injury.	
Additional Definitions		
Adverse Event (AE)	An Adverse Event (AE) is an untoward medical occurrence, unintended disease or injury, or untoward clinical signs (including abnormal laboratory findings) in subjects, users or other persons, whether or not related to the investigational medical device and whether anticipated or unanticipated (ISO 14155:2020, 3.2).  NOTE 1: This definition includes events related to the investigational medical device.  NOTE 2: This definition includes events related to the procedures involved.	
Serious Adverse Event (SAE)	
 
An AE that led to any of the following:
 
death,
 
serious deterioration in the health of the subject, users or other persons as defined by one or more of the following:
 
	

Term	Definition
ierm	
 
a life-threatening illness or injury, or
 
a permanent impairment of a body structure or a body function, including chronic disease, or
 
in-patient or prolonged hospitalization, or
 
medical or surgical intervention to prevent life- threatening illness or injury or permanent impairment to a body structure or a body function,
 
fetal distress, fetal death or a congenital abnormality or birth defect including physical or mental impairment
 
NOTE 1: Planned hospitalization for a pre-existing condition, or a procedure required by the CIP, without serious deterioration in health, is not considered an SAE. (ISO
 

Minor Complications (SIR Classification)	
 
14155:2020, 3.45)
 
Minor complications:
 
No therapy, no consequence
 
Nominal therapy, no consequence (includes overnight admission for observation only)
 

Major Complications (SIR Classification)	
 
Major complications:
 
Require therapy, minor hospitalization (≤ 48 hours)
 
Require major therapy, unplanned increase in level of care, prolonged hospitalization (>48 hours)
 
Permanent adverse sequelae
 
Death
 

Adverse Device Effect (ADE)	AE related to the use of an investigational medical device  NOTE 1: This definition includes AEs resulting from insufficient or inadequate instructions for use, deployment, implantation, installation, or operation, or any malfunction of the investigational medical device.  NOTE 2: This definition includes any event resulting from an error use or from intentional misuse of the investigational medical device.  NOTE 3: this includes 'comparator' if the comparator is a medical device. (ISO 14155:2020, 3.1)
Serious Adverse Device Effect (SADE) Unanticipated Serious Adverse Device Effect (USADE) (pre-market term only)	Adverse device effect that has resulted in any of the consequences characteristic of a serious adverse event. (ISO 14155:2020, 3.44)  USADE is a serious adverse device effect which by its nature, incidence, severity or outcome has not been identified in the current risk assessment. (ISO 14155:2020, 3.51)
Anticipated Serious Adverse Device Effect (ASADE) (pre-market term only) Unanticipated Adverse Device Effect (UADE) (pre-market term only)	ASADE is a serious adverse device effect which by its nature, incidence, severity or outcome has been identified in the risk assessment. (ISO 14155:2020, 3.51)  Any serious adverse effect on health or safety or any life- threatening problem or death caused by, or associated with, a device, if that effect, problem, or death, was not previously identified in a nature, severity, or degree of incidence in the investigational plan or application (including a supplementary plan or application), or any other unanticipated serious problem associated with a device that relates to the rights, safety, or welfare of subjects. (21 CFR 812.3(s))

Term	Definition
Device Deficiency	Inadequacy of a medical device with respect to its identity, quality, durability,
	reliability, usability, safety or performance.
	NOTE 1: Device Deficiencies include malfunctions, use errors and inadequacy in the
	information supplied by the manufacturer including labeling.
	NOTE 2: This definition includes device deficiencies related to the
	investigational medical device or the comparator. (ISO 14155:2020, 3.19)
High-Risk PE	Per ESC guidelines 2019: High-Risk PE determined by hemodynamic instability, PESI III-
	V or sPESI ≥ 1, RV Dysfunction, and Elevated cardiac troponins.
	Note Definition of hemodynamic instability, which delineates acute high-risk
	pulmonary embolism (one of the following clinical manifestations at presentation). 1.
	Cardiac Arrest: Need for cardiopulmonary resuscitation, 2. Obstructive Shock: Systolic
	BP < 90 mmHg or vasopressors required to achieve a BP ≥ 90 mmHg despite adequate
	filling status AND End-organ hypoperfusion (altered mental status; cold, clammy skin;
	oliguria/anuria; increased serum lactate), OR 3. Persistent Hypotension: Systolic BP <
	90 mmHg or systolic BP drop ≥ 40 mmHg, lasting longer than 15 min and not caused by
	new-onset arrhythmia, hypovolemia, or sepsis.
Intermediate High-Risk	Per ESC guidelines 2019: Intermediate High-Risk PE determined by no hemodynamic
PE	instability, PESI III- V or sPESI ≥ 1, RV Dysfunction, and Elevated cardiac troponins.
Intermediate Low-Risk	Per ESC guidelines 2019: Intermediate Low-Risk PE determined by no hemodynamic
PE	instability, PESI III- V or sPESI ≥ 1, and 1 or none of the following: RV Dysfunction;
	Elevated cardiac troponins.
Patient/ Subject	Participants in the study.
Recurrent PE	Symptomatic worsening from baseline of the embolism that was successfully treated
	with the index procedure with documentation of a change on CTPA or other suitable
	imaging modality, as determined by the CEC.

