### 3.1 FLARE STUDY

The FLARE study, IDE # G160002, was a prospective, single-arm, multicenter study conducted at 18 sites across the United States from April 2016 to November 2017. The study evaluated the treatment of 106 patients with intermediate risk PE using the FlowTriever System. The study met both of its primary endpoints, which demonstrated safety and effectiveness and represented a successful treatment of PE. Data from the study supported FDA 510(k) clearance (K180466) for the FlowTriever System.

All patients enrolled in the study were symptomatic for 14 days or less, with clinical signs and presentation consistent with PE, including documented proximal PE by computed tomography, or CT, angiography, and a site-reported right ventricle/left ventricle, or RV/LV, ratio of 0.9 or greater by CT.

The primary effectiveness endpoint was a reduction in core laboratory-assessed RV/LV ratio. The average RV/LV ratio decreased from 1.53 (n = 104) at baseline assessment to 1.15 (n = 101) in the 48 hours after treatment using the FlowTriever, representing a statistically significant reduction in RV/LV ratio of 0.38 on average (25.1%; p < 0.0001).

The primary safety endpoint was measured by device-related death, major bleeding, treatment-related clinical deterioration, pulmonary vascular injury or cardiac injury in the 48 hours after treatment using the FlowTriever. Four patients (3.8%) experienced six major adverse events in the 48 hours after treatment. All major adverse events were determined to be procedure related, with no device-related major adverse events. All four (3.8%) patients exhibited clinical deterioration. There was one major bleeding event (0.9%) and one pulmonary vascular injury. The major bleeding event experienced by one patient was also classified as a pulmonary vascular injury and as clinical deterioration.

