Two patients (1.9%) experienced respiratory deterioration during or immediately after the procedure that required emergent intubation. One patient (0.9%) became agitated during the procedure, requiring increased sedation, and had a ventricular fibrillation event that required cardioversion and emergent intubation. An additional 10 patients experienced serious adverse events within 30 days after treatment, none of which were determined to be procedure- or device-related. In total, 14 patients (13.2%) experienced 26 serious adverse events within 30 days, with five patients (4.7%) experiencing multiple serious adverse events. One patient (0.9%) died within 30 days of treatment because of respiratory failure from undiagnosed metastatic breast cancer.

FLARE Study results were published in Tu T, et al. A Prospective, Single-Arm, Multicenter Trial of Catheter-Directed Mechanical Thrombectomy for Intermediate-Risk Acute Pulmonary Embolism: The FLARE Study. JACC Cardiovasc Interv 2019.

**CONFIDENTIAL** Page 21 of 60 FLARE-FT2 Study

Inari Medical Version 4.0 FlowTriever2 Catheter 11-Aug-2023

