# 4.2 PRIMARY ENDPOINT - SAFETY

The study's primary safety endpoint is incidence of adjudicated Serious Adverse Events (SAE), which is a composite of:

- Mortality through 48 hours after the index procedure related to FlowTriever2 Catheter
- Major bleeding through 48 hours after the index procedure related to FlowTriever2 Catheter
- Intra-procedural device or procedure-related adverse events, including:
  - Clinical deterioration defined by hemodynamic or respiratory worsening
  - Pulmonary vascular injury related to FlowTriever2 Catheter
  - Cardiac injury related to FlowTriever2 Catheter

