## 9 STATISTICS & DATA ANALYSIS

#### 9.1 SAMPLE SIZE CALCULATIONS

The sample size of 50 subjects reflects sample size to confirm the FlowTriever2 Catheter performance. The sample size of 50 subjects was estimated in order to provide at least 80% power with one-sided alpha = 0.05 for assuming FT2 safety event proportions of 11% vs. the performance goal of 25% from FLARE. Sensitivity analysis for this confirmatory study will be performed on a sub-population of the 50 subjects that did not receive adjunctive thrombolytics. Descriptive statistics on safety and effectiveness will be provided for all patients.

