5.1. Sample Size

The sample size of 50 subjects was adopted to confirm the FlowTriever2 Catheter performance. Given the sample size, at least 80% power can be achieved under one-sample fixed design with one-sided alpha = 0.05 for assuming observed FT2 safety event proportions of 11% compared to the hypothesized performance goal of 25% from FLARE. Descriptive statistics on safety and effectiveness endpoints will be provided based on all subjects to conclude the study objectives, no hypothesis testing was relied. Sensitivity analysis will be performed on a sub-population of the 50 subjects that did not receive adjunctive thrombolytics.

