5.2. Primary Safety Endpoint Analysis

The primary safety endpoint analysis is performed by assessing the incidence rate of the composite endpoint of SAE, including device-related mortality through 48 hours, device-related major bleeding through 48 hours, intra-procedural device or procedure-related adverse events.

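### Clinical deterioration counts toward primary safety only when intra-procedural, with no procedure end or onset rule, while the 25% goal comes from a composite described over 48 hours

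*Protocol*

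**What the plan says.** Protocol 4.2 and 9.3 and SAP 2.1 build the primary safety composite in two parts. Death and major bleeding, each related to the FlowTriever2 Catheter, count through 48 hours. Clinical deterioration, pulmonary vascular injury and cardiac injury sit under "Intra-procedural device or procedure-related adverse events, including". SAP 5.2 keeps the limit when it names the third component as "intra-procedural device or procedure-related adverse events".

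Protocol 12 and SAP 6 define clinical deterioration by a list of treatment-related examples. Two of them need time to establish: hypotension, worded as "arterial hypotension (>1 hour or requiring vasopressors) or shock", and a worsening of oxygenation that persists. The footnotes to Table 1 (Protocol 6.2) set Time 0 at entry of the FlowTriever2 Catheter. Neither document defines the end of the procedure or says whether a deterioration event must begin, or must meet its criterion, before that end.

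The yardstick is in Protocol 9.1: "assuming FT2 safety event proportions of 11% vs. the performance goal of 25% from FLARE". SAP 5.1 repeats it. Protocol 3.1 describes the FLARE primary safety endpoint as device-related death, major bleeding, treatment-related clinical deterioration, "pulmonary vascular injury or cardiac injury in the 48 hours after treatment using the FlowTriever". Protocol 3.2 tests that endpoint against 25%.

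**The concern.** The FT2 composite covers less time for deterioration than the composite behind its goal, and deterioration dominated FLARE: all four FLARE patients with a major adverse event had it (Protocol 3.1). If some deterioration is recognised only after the procedure, the FT2 rate could be lower because of what is counted, not because of how the device performs.

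The secondary endpoints would not reliably recover such events. Protocol 4.4 names all-cause death, device-related SAEs and symptomatic recurrent PE, each through the 30-day visit. In FLARE every major adverse event was judged procedure-related and none device-related. A procedure-related, non-device, non-fatal deterioration after the procedure therefore belongs to no named primary or secondary endpoint unless it meets another component.

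**Working it through.** **1. The plan's own figure.** Inputs (Protocol 9.1, SAP 5.1): n = 50, assumed event rate 11%, goal 25%, one-sided alpha 0.05, one-sample fixed design. With an exact binomial test, the largest passing count is 7:

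- P(X ≤ 7 | n = 50, p = 0.25) = 0.0453
- P(X ≤ 7 | n = 50, p = 0.11) = 0.8207

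The stated power of at least 80% reproduces. The arithmetic is sound; the question is whether the two rates count the same events.

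**2. The windows side by side.**

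| Component | FT2 (Protocol 4.2) | FLARE (Protocol 3.1) |
|---|---|---|
| Death | FlowTriever2-related, 48 hours | Device-related, 48 hours |
| Major bleeding | FlowTriever2-related, 48 hours | 48 hours, no device limit stated |
| Clinical deterioration | Intra-procedural, device- or procedure-related | Treatment-related, 48 hours |
| Vascular or cardiac injury | Intra-procedural, FlowTriever2-related | 48 hours |

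**3. FLARE limits.** The exact one-sided 95% upper limit for k events in n is the 0.95 quantile of Beta(k + 1, n − k).

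- 4/104 = 3.8%, limit 8.6% (matches the mITT limit in Protocol 3.2)
- 4/106 = 3.8%, limit 8.4% (matches the ITT limit)

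**4. What an intra-procedural rule could have done in FLARE.** Protocol 3.1 says that two patients "experienced respiratory deterioration during or immediately after the procedure that required emergent intubation". It does not divide them between the two periods, so the split is an assumption:

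- both during the procedure: 4/106 = 3.8% (limit 8.4%), no change from these two
- one after it: 3/106 = 2.8%
- both after it and not counted: 2/106 = 1.9% (limit 5.8%); on the mITT denominator, 2/104 = 1.9% (limit 5.9%)

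**5. What it could do to a reading against 25%.** Suppose the true 48-hour composite rate equals 25% and a share f of those events is post-procedure deterioration that is not counted. The documents do not give f. The counted rate is 0.25 × (1 − f), and the chance of 7 or fewer events in 50 is:

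| f | Counted rate | P(X ≤ 7) |
|---|---|---|
| 0 | 25.0% | 0.0453 |
| 10% | 22.5% | 0.0977 |
| 20% | 20.0% | 0.1904 |
| 25% | 18.75% | 0.2553 |
| 50% | 12.5% | 0.7165 |

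No such test is planned, so these are not error rates of the study. They show how quickly a comparison with 25% loses meaning once the windows differ.

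**The case against.** The best defence has five parts.

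- **The definition is a list of alternatives.** Vasopressor need, intubation, shock and resuscitation can all occur on the table. This stands. A reader might infer that deterioration usually becomes established only after the catheter is out; the documents give no timing data to support that.
- **Loss is not certain.** A reader might infer that all post-procedure deterioration is excluded. If onset governs, hypotension that starts on the table and passes one hour in recovery still counts, and the Clinical Events Committee may apply such a rule under its charter, which is not among the documents. This also stands, but it leaves the classification of a primary endpoint to a rule that neither the protocol nor the SAP states.
- **The wording has a precedent.** The FLASH composite in Protocol 3.3 also lists deterioration as intra-procedural, and the FLARE window rests on a summary sentence. The likely explanation is a definition carried over from the registry. Even so, the 25% is cited from FLARE.
- **The analysis is descriptive.** SAP 2 says the endpoints will not determine study success, and SAP 5.1 relies on no hypothesis test. A reader might infer an inflated type I error; there is no test whose error could be inflated. The rate is still the primary safety result, and 25% is the only benchmark given for it.
- **Later events are still recorded and adjudicated** (Protocol 6.2.3, 8.2, 8.7). True, and that is why the change is cheap.

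**Conclusion.** The concern holds as a mismatch of windows together with an undefined boundary. As written, the FT2 composite may give a lower rate than a FLARE-type composite in the same patients, and it should not be read against 25% or 3.8% without that caveat.

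The size cannot be determined from the documents. The FLARE illustration runs from no change to a halving (3.8% to 1.9%), and the halving depends wholly on assuming that both ambiguous cases came after the procedure. A reader might take the halving as an estimate; it is only one end of the range.

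A reader might also want the same 48-hour window for pulmonary vascular and cardiac injury. Protocol 12 and SAP 6 tie both injuries to the index procedure itself, which is a coherent window for catheter trauma, so the point is confined to clinical deterioration.

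**What to change.** In Protocol 4.2 and 9.3 and SAP 2.1 and 5.2, with the synopsis to match:

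1. Count device- or procedure-related clinical deterioration with onset from Time 0 (FlowTriever2 Catheter entry) through 48 hours. State that onset governs, so that a time-dependent criterion may be met later. Time 0 is the right start because enrollment itself depends on catheter entry (Protocol 5.3, 5.4); starting at first venous access would reach back before subjects are enrolled.
2. Define the end of the procedure and show the intra-procedural count as a sub-row.
3. Set the 48-hour composite, not the intra-procedural one, beside the 25% goal.
4. Leave pulmonary vascular and cardiac injury as defined.
5. Note in the report that FT2 limits major bleeding to FlowTriever2-related events, a limit not stated for FLARE in Protocol 3.1. The amended composite would still differ from FLARE in this respect.

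The cost is an amendment to the primary endpoint wording, with IRB approval under Protocol 10.1.1. Adverse events are already collected and adjudicated over this period, and subjects discharged before 48 hours already receive a call about SAEs. The sub-row needs onset recorded precisely enough to place it before or after the end of the procedure. The downside is that the composite rate may be slightly less favourable.
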